10.5 Record Maintenance/Retention

The Investigator will retain the originals of all source documents generated at the location where the study is being conducted, either: 1) until after regulatory agency approval is obtained for the study medication in the country/countries in which the results of this study comprise the submission dossier, or 2) for a period of 2 years after the report of the study has been finalized, in the absence of a regulatory approval. After that time, all study-related documents will be archived according to ICH GCP regulations.

11 FINANCE AND INSURANCE

Financial arrangements are detailed in the Investigator Agreement between the Sponsor and Investigator.

The Sponsor will arrange clinical study insurance to compensate patients for any potential injury or death caused by the study.

12 PUBLICATION POLICY

The publication policy is detailed in the Investigator Agreement between the Sponsor and Investigator.

14 APPENDICES

14.1 Birth Control Methods For Women of Childbearing Potential Which May Be Considered As Highly Effective

(Adapted from the Clinical Trial Facilitation Group, Heads of Medicines Agencies, 2014)

I. Definitions

Woman of Childbearing Potential

A woman is considered fertile following menarche and until becoming postmenopausal unless permanently sterile. Permanent sterilization methods include hysterectomy, bilateral salpingectomy, and bilateral oophorectomy.

Women in the following categories are not considered women of childbearing potential:

1. Premenopausal female with one of the following:

- Documented hysterectomy.
- Documented bilateral salpingectomy.
- Documented bilateral oophorectomy.

Note: Documentation can come from the study center staff's: review of participant's medical records, medical examination, or medical history interview.

2. Premenarchal.

3. Postmenopausal female:

- Females who are postmenopausal (age-related amenorrhea ≥ 12 consecutive months and increased FSH >40 mIU/mL), or who have undergone hysterectomy or bilateral oophorectomy are exempt from pregnancy testing. If necessary to confirm postmenopausal status, an FSH will be drawn at Screening.
- Females on hormone replacement therapy (HRT) and whose menopausal status is in doubt will be required to use one of the non-hormonal highly effective contraception methods if they wish to continue their HRT during the study. Otherwise, they must discontinue HRT to allow confirmation of postmenopausal status before study enrollment.

II. Methods

For the purpose of this guidance, methods that can achieve a failure rate of less than 1% per year when used consistently and correctly are considered as highly effective birth control methods. Such methods include:

- Combined (estrogen and progestogen containing) hormonal contraception associated with inhibition of ovulation:
 - Oral
 - Intravaginal
 - Transdermal

- Progestogen-only hormonal contraception associated with inhibition of ovulation¹:
 - Oral
 - Injectable
 - Implantable¹
- Intrauterine device¹
- Intrauterine hormone-releasing system¹
- Bilateral tubal occlusion¹
- Vasectomized partner^{1,2}
- Sexual abstinence³

¹ Contraception methods that in the context of this guidance are considered to have low user dependency

² Vasectomized partner is a highly effective birth control method provided that partner is the sole sexual partner of the trial participant and that the vasectomized partner has received medical assessment of the surgical success

³ In the context of this guidance sexual abstinence is considered a highly effective method only if defined as refraining from heterosexual intercourse during the entire period of risk associated with the study treatments. The reliability of sexual abstinence needs to be evaluated in relation to the duration of the clinical trial and the preferred and usual lifestyle of the patient

14.2 12-lead ECG Requirement for Inclusion

The ECG obtained at Screening must be free from any of the following abnormalities:

- Sinus tachycardia ≥ 110 bpm (Sinus tachycardia ≥ 110 bpm should be confirmed by 2 additional readings at least 5 minutes apart.)
- Sinus bradycardia < 45 bpm (Sinus bradycardia < 45 bpm should be confirmed by 2 additional readings at least 5 minutes apart)
- Multifocal atrial tachycardia
- Junctional (heart rate > 100 bpm)
- Junctional escape complexes
- Supraventricular tachycardia (> 100 bpm)
- Ventricular tachycardia
- Atrial fibrillation with rapid ventricular response (rate > 100 bpm)
- Atrial flutter
- Bigeminy, trigeminy or multifocal premature ventricular complexes
- Ventricular flutter
- Ventricular fibrillation
- Torsades de Pointes
- R on T phenomenon
- Wide QRS tachycardia (diagnosis unknown)
- Electrical alternans
- Pacemaker
- Idioventricular rhythm – heart rate < 100 bpm
- Mobitz type II second degree or third degree atrioventricular (AV) block
- AV dissociation
- Bifascicular Block

- Trifascicular Block
- Left bundle branch block
- Subjects without complete right bundle branch block: QTc(F) \geq 450msec or an ECG that is unsuitable for QT measurements (e.g. poorly defined termination of the T wave)

14.3 Interpreting Adverse Event Causality

The following factors should be considered when deciding if there is a "reasonable possibility" that an adverse event may have been caused by the study medication.

- Time Course. Exposure to suspect study medication. Has the subject actually received the suspect study medication? Did the adverse event occur in a reasonable temporal relationship to the administration of the suspect study medication?
- Consistency with known study medication profile. Was the adverse event consistent with the previous knowledge of the suspect study medication (pharmacology and toxicology) or drugs of the same pharmacological class? OR Could the adverse event be anticipated from its pharmacological properties?
- Dechallenge experience. Did the adverse event resolve or improve on stopping or reducing the dose of the suspect study medication?
- No alternative cause. The adverse event cannot be reasonably explained by another etiology such as the underlying disease, other drugs, other host or environmental factors
- Rechallenge experience. Did the adverse event reoccur if the suspected study medication was reintroduced after having been stopped
- Laboratory tests. A specific laboratory investigation (if performed) has confirmed the relationship?

A "reasonable possibility" could be considered to exist for an adverse event where one or more of these factors exist.

In contrast, there would not be a "reasonable possibility" of causality if none of the above criteria apply or where there is evidence of exposure and a reasonable time course, but any dechallenge (if performed) is negative or ambiguous or there is another more likely cause of the adverse events.

In difficult cases, other factors could be considered such as:

- Is this a recognized feature of overdose of the study medication?
- Is there a known mechanism?

Ambiguous cases should be considered as being a "reasonable possibility" of a causal relationship unless further evidence becomes available to refute this. Causal relationship in cases where the disease under study has deteriorated due to lack of effect should be classified as no reasonable possibility.

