A suspected unexpected serious adverse reactions (SUSAR) is any suspected adverse reaction related to the study medication that is both unexpected and serious.

Standard procedures for emergency care should be followed for any individual adverse event, whenever clinically needed (decision to be taken by the Investigator).

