7.4.1.2.3 Causality

The Investigator will assess causal relationship between the study medication and each adverse event, and answer "yes" or "no" to the question, "Do you consider that there is a reasonable possibility that the event may have been caused by the study medication?"

For SAEs, causal relationship will also be assessed for study procedures, additional study medication, and other medication. Note that for SAEs that could be associated with any study procedure, the causal relationship is implied as "yes".

A guide to the interpretation of the causality question is found in Section 14.3.

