7.4.1.2.4 Action and Outcome

- Action taken with study medication (none, study medication stopped, study medication temporarily interrupted)
- Other actions (none, concomitant medication, study discontinuation, hospitalization, other)
- The outcome and date of outcome according to the following definitions:
 - Recovered or resolved (adverse event disappeared)
 - Recovering or resolving (patient is recovering)
 - Not recovered or not resolved (adverse event remains without signs of improvement)
 - Recovered or resolved with sequelae (adverse event has resulted in permanent disability or incapacity)
 - Fatal
 - Unknown (only applicable if patient has been lost to follow-up)

- Seriousness (yes or no)

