17.1. Adverse Events

AEs will be listed for ENR set, with patients classified according to actual treatment received, and summarized for SAF set.

AEs will be coded using the MedDRA central coding dictionary, Version 22.0.

Treatment emergent adverse events (TEAEs) are defined as all AEs which start after the first dose of study treatment or start prior to first dose of study treatment and worsen, based on the investigator's assessment of severity, on or after first dose of study treatment.

Non-treatment emergent adverse events (non-TEAEs) are defined as AEs that start prior to first dose of study treatment and end prior to first dose of study treatment, or do not worsen, based on the investigator's assessment of severity, on or after first dose of study treatment.

In the case where it is not possible to define an AE as treatment emergent or not, the AE will be classified by the worst case; i.e. treatment emergent.

If any AE records contain only partial dates, these will be handled by imputation, as described in the Appendix 2.

Document: ...\\Verona_Pharma\\RPL554\\BZA48916\\Biostatistics\\Documentation\\SAP\\Verona CO-205 SAP v1.0

Author: [REDACTED] Version Number: V1.0

Version Date: 05DEC2019

Template No.: CS_TP_BS016 Revision 5

Reference: CS_WI_BS005

Effective Date: 01Apr2018

An overall summary of the number of patients with at least one event in each of the categories listed below will be provided as specified in the templates. In addition, the number of patients with each of the following AE events will be presented by SOC and PT and summarized by treatment group:

- TEAE
- TEAEs leading to discontinuation of study treatment
- TEAEs causally related to study treatment
- TEAEs by maximum severity
- Serious TEAEs
- Serious TEAEs causally related to study treatment
- Serious TEAEs by maximum severity
- Serious TEAEs leading to discontinuation of study treatment
- TEAEs with an outcome of death

AEs will be identified by using the 'Adverse Events' page of the eCRF. Listings will include TEAEs and Non-TEAEs.

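### Protocol Section 14.3 gives opposite causality answers for an adverse event with plausible timing and an ambiguous dechallenge, and does not say which sentence prevails

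*Protocol*

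**What the plan says.** Protocol Section 7.4.1.2.3 asks the investigator to answer yes or no to "Do you consider that there is a reasonable possibility that the event may have been caused by the study medication". It then points to the appendix: "A guide to the interpretation of the causality question is found in Section 14.3".

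Section 14.3 lists factors to consider, among them time course, fit with the known profile, dechallenge and the absence of another cause. It then gives three instructions:

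- **A, the positive sentence:** "A 'reasonable possibility' could be considered to exist for an adverse event where one or more of these factors exist".
- **B, the negative sentence:** there would be no reasonable possibility if none of the factors applies, or where there is "evidence of exposure and a reasonable time course, but any dechallenge (if performed) is negative or ambiguous", or where another cause is more likely.
- **C, the default**, placed after a short paragraph on difficult cases: "Ambiguous cases should be considered as being a 'reasonable possibility' of a causal relationship unless further evidence becomes available to refute this".

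On use of the answer, Protocol Section 9.4.7 and SAP Section 17.1 tabulate causally related events by treatment group. The SAP list includes "Serious TEAEs causally related to study treatment". Protocol Section 7.4.1.1 defines a SUSAR as "any suspected adverse reaction related to the study medication that is both unexpected and serious", and Section 7.4.1.3 gives the determination to the sponsor's Medical Monitor.

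**The concern.** B and C both use the word *ambiguous* and point in opposite directions. An investigator who stops study medication for an event, and cannot tell from what follows whether stopping helped, finds one sentence leading to no and a later one leading to yes.

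The direction matters. An inconclusive dechallenge carries little information either way, yet B treats it like a negative one. That moves the event out of the related category, which is the less cautious outcome for a safety table.

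The plan uses approximately 50 centers. The documents describe no central adjudication of causality, and SAP Section 4.1 states that there is no data monitoring committee. For non-serious events, nothing described downstream would even out differences in how sites read the guide.

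**Working it through.** No arithmetic applies, and the plan gives no figure to reproduce. The check sets the sentences side by side and applies them to defined cases.

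**When a dechallenge exists.** Section 14.3 describes it as whether the event resolved or improved on stopping or reducing the dose. Section 7.4.1.2.4 records "Action taken with study medication (none, study medication stopped, study medication temporarily interrupted". The cases in question are therefore events where study medication was stopped or interrupted and the result was unclear. They are not all events that led to stopping. Section 4.4.2 requires discontinuation for intolerable or persistent adverse events, so some dechallenges are to be expected.

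**Applying A, B and C.** Each case has exposure and a plausible time course.

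| Case | A (one or more factors) | B (negative sentence) | C (default) |
|---|---|---|---|
| 1. No dechallenge, no more likely cause | permits yes | not triggered | yes, if the case is judged ambiguous |
| 2. Dechallenge ambiguous | permits yes | no | yes, if the case is judged ambiguous |
| 3. Dechallenge negative | permits yes | no | does not address it |
| 4. Another cause more likely | permits yes | no | does not address it |

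**Reading the table.**

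1. Case 2 is the conflict: B says no, C says yes, and A allows yes because time course is itself a listed factor.
2. Compare cases 1 and 2. B's dechallenge limb applies only if a dechallenge was performed. An event that may be coded yes with no dechallenge becomes no under B once an uninformative one is added. A result that adds nothing lowers the classification.
3. C sets aside the yes answer only when further evidence refutes it. An ambiguous dechallenge refutes nothing, so B and C also differ on what evidence is needed to reach no.
4. In cases 3 and 4, C is not in play, but A and B still pull apart. A is permissive and B is directive, and their relation is not stated.

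**Consistency with the rest of the plan.** Where other adverse event attributes are uncertain, the SAP takes the worst case. An event whose treatment emergence cannot be determined counts as treatment emergent (Section 17.1), and a missing severity counts as severe (Section 17.1.1). C follows that convention; the ambiguous limb of B does not.

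**The case against.** The strongest reply is that this is a tension in wording and not an unavoidable contradiction. *Ambiguous* describes the dechallenge in B and the whole case in C. A reader could apply the specific sentence first and keep the default for cases still unclear after everything has been weighed. Section 14.3 is called a guide, and the operative test is the investigator's own judgement. This is a fair reading, but the text does not state it, and it leaves the result in the comparison of cases 1 and 2.

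Four stronger inferences are tempting, and the documents do not support them:

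- **That SUSAR decisions turn on this sentence.** The Medical Monitor determines SUSARs, and nothing says the monitor applies Section 14.3. All SAEs go to the sponsor within 24 hours, whatever the causality answer.
- **That B sends events fitting the known profile, such as dizziness or palpitations, to no.** B names only exposure and timing, so it can be read as covering events with no other support. The point is contestable and is not relied on here.
- **That comparisons of related discontinuations between arms are distorted.** The SAP lists discontinuations and causally related events as separate categories, not in combination. Section 17 plans no statistical comparison of safety data unless specified, and Section 17.1 specifies none.
- **That an ambiguous dechallenge is frequent.** The documents give no rate for it, nor for withdrawals due to adverse events.

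It also stands that no event is hidden. All TEAEs, serious TEAEs and TEAEs leading to discontinuation are tabulated regardless of causality. Investigators are blinded, and the same wording applies in every arm.

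**Conclusion.** The point holds for a limited class: events with exposure, a plausible time course and an ambiguous dechallenge. For these, Section 14.3 supports both answers without ranking its sentences. The code can differ between sites, and an uninformative dechallenge can move an event to not related.

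The effect is confined to the related and serious related TEAE tables. It may reach the SUSAR determination as one input. Efficacy, power, alpha and sample size are untouched. The number of affected events cannot be derived from the documents, and no count is offered. The conclusion does not need one, because the conflict arises with the first such event. It rests on one assumption: that investigators use Section 14.3 as Section 7.4.1.2.3 directs. This is a modest inconsistency that is cheap to correct and worth correcting.

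**What to change.** 1. In Section 14.3, delete the words *or ambiguous* from the sentence describing when there is no reasonable possibility. An ambiguous dechallenge then falls under the section's own default.
2. Add a sentence saying how the one-or-more-factors sentence interacts with a negative dechallenge or a more likely other cause. The deletion alone leaves that question open.
3. If causality answers are queried before database lock, do it blinded, word the query neutrally, and cover every adverse event where study medication was stopped or interrupted. Querying only the events coded no could move answers in one direction only.

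The cost is a small protocol amendment, with approval under Section 10.2 if it is judged substantial, and a short query list if step 3 is used. The downside is that a few more events may be counted as related.

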14.4 Tiotropium Prescribing Highlights and Instructions for Use

Note: The information below is excerpted from the US package insert for tiotropium. Full prescribing information in the US is available at:

<https://docs.boehringer-ingelheim.com/Prescribing%20Information/PIs/Spiriva%20Respimat/spirivarespimat.pdf#page=15>

HIGHLIGHTS OF PRESCRIBING INFORMATION

These highlights do not include all the information needed to use SPIRIVA RESPIMAT safely and effectively. See full prescribing information for SPIRIVA RESPIMAT.

SPIRIVA® RESPIMAT® (tiotropium bromide) inhalation spray, for oral inhalation

Initial U.S. Approval: 2004

INDICATIONS AND USAGE

SPIRIVA RESPIMAT is an anticholinergic indicated for:

- The long-term, once-daily, maintenance treatment of bronchospasm associated with chronic obstructive pulmonary disease (COPD), and for reducing COPD exacerbations (1.1)
- The long-term, once-daily, maintenance treatment of asthma in patients 6 years of age and older (1.2)

Limitation of Use:

- Not indicated for relief of acute bronchospasm (1.1, 1.2, 5.1)

DOSAGE AND ADMINISTRATION

For oral inhalation only

To receive the full dose of medication, SPIRIVA RESPIMAT must be administered as two inhalations once-daily.

- Treatment of COPD: 2 inhalations of SPIRIVA RESPIMAT 2.5 mcg once-daily (2)
- Treatment of asthma patients 6 years and older: 2 inhalations of SPIRIVA RESPIMAT 1.25 mcg once-daily (2)

DOSAGE FORMS AND STRENGTHS

- Inhalation spray: 1.25 mcg or 2.5 mcg tiotropium per actuation with the SPIRIVA RESPIMAT inhaler. Two actuations equal one dose (2.5 mcg or 5 mcg). (3)

CONTRAINDICATIONS

Hypersensitivity to tiotropium, ipratropium, or any component of this product (4)

WARNINGS AND PRECAUTIONS

- Not for acute use, i.e., not a rescue medication (5.1)
- Immediate hypersensitivity reactions: Discontinue SPIRIVA RESPIMAT at once and consider alternatives if immediate hypersensitivity reactions, including angioedema, urticaria, rash, bronchospasm, or anaphylaxis, occur. (5.2)
- Paradoxical bronchospasm: Discontinue SPIRIVA RESPIMAT and consider other treatments if paradoxical bronchospasm occurs. (5.3)
- Worsening of narrow-angle glaucoma may occur. Use with caution in patients with narrow-angle glaucoma and instruct patients to consult a physician immediately if this occurs. (5.4)
- Worsening of urinary retention may occur. Use with caution in patients with prostatic hyperplasia or bladder-neck obstruction and instruct patient to consult a physician immediately if this occurs. (5.5)

ADVERSE REACTIONS

The most common adverse reactions in:

- COPD: (>3% incidence in the placebo-controlled trials with treatment durations of between 4 and 48 weeks) were pharyngitis, cough, dry mouth, and sinusitis (6.1).
- Asthma: (>2% incidence in the placebo-controlled trials with treatment durations of between 12 and 52 weeks) were pharyngitis, headache, bronchitis, and sinusitis in adults (6.2).

To report SUSPECTED ADVERSE REACTIONS, contact Boehringer Ingelheim Pharmaceuticals, Inc. at [contact] or [contact] TTY or FDA at [name] or www.fda.gov/medwatch.

DRUG INTERACTIONS

Anticholinergics: May interact additively with concomitantly used anticholinergic medications. Avoid administration of SPIRIVA RESPIMAT with other anticholinergic-containing drugs. (7.2)

USE IN SPECIFIC POPULATIONS

Patients with moderate to severe renal impairment should be monitored closely for potential anticholinergic side effects. (2, 8.6)

See 17 for PATIENT COUNSELING INFORMATION and FDA-approved patient labeling.

Revised: 2/2019

Instructions for Use

SPIRIVA® RESPIMAT® (speh REE
val - RES peh mat) (tiotropium
bromide)

inhalation spray, for oral inhalation

For oral inhalation only

Do not spray SPIRIVA RESPIMAT into your eyes.

Read this Instructions for Use before you start using SPIRIVA RESPIMAT and each time you get a refill. There may be new information. This leaflet does not take the place of talking to your doctor about your medical condition or your treatment.

You will need to use this inhaler 1 time each day, at the same time each day. Each time you use it take 2 puffs.

[figure not shown]
Use SPIRIVA RESPIMAT exactly as prescribed by your doctor. Do not change your dose or how often you use SPIRIVA RESPIMAT without talking with your doctor. Children should use SPIRIVA RESPIMAT with the help of an adult, as instructed by their doctor.

Tell your doctor about all of the medicines you take, including prescription and over-the-counter medicines, vitamins, and herbal supplements. SPIRIVA RESPIMAT may affect the way some medicines work and some other medicines may affect the way SPIRIVA RESPIMAT works. Do not use other inhaled medicines with SPIRIVA RESPIMAT without talking to your doctor.

The SPIRIVA RESPIMAT inhaler has a slow moving mist that helps you inhale the medicine.

Do not turn the clear base before inserting the cartridge.

Your SPIRIVA RESPIMAT may have either an aqua or a blue cap, depending on the strength prescribed by your doctor. The steps shown below should be followed.

How to store your SPIRIVA RESPIMAT inhaler

- Store SPIRIVA RESPIMAT at room temperature between 68°F to 77°F (20°C to 25°C).
- **Do not** freeze your SPIRIVA RESPIMAT cartridge and inhaler.
- If SPIRIVA RESPIMAT has not been used for more than 3 days, release 1 puff towards the ground.
- If SPIRIVA RESPIMAT has not been used for more than 21 days, repeat steps 4 to 6 under the “Prepare for first use” until a mist is visible. Then repeat steps 4 to 6 three more times.
- **Keep your SPIRIVA RESPIMAT cartridge, inhaler, and all medicines out of the reach of children.**

How to care for your SPIRIVA RESPIMAT inhaler

Clean the mouthpiece, including the metal part inside the mouthpiece, with a damp cloth or tissue only, at least 1 time each week. Any minor discoloration in the mouthpiece does not affect your SPIRIVA RESPIMAT inhaler.

[figure not shown]
When to get a new SPIRIVA RESPIMAT inhaler

- The scale on your inhaler shows the number of puffs in the inhaler. You should use 2 puffs 1 time each day.
- The dose indicator shows approximately how many puffs are left in the inhaler.
- When the dose indicator enters the red area of the scale you need to refill your prescription as soon as possible.
- When the dose indicator reaches the end of the red scale, your SPIRIVA RESPIMAT is empty and automatically locks. At this point, the clear base cannot be turned any further.

[figure not shown]

- Three months after insertion of cartridge, throw away the SPIRIVA RESPIMAT even if it has not been used, or when the inhaler is locked, or when it expires, whichever comes first.

Prepare for first use

1. Remove clear base	
 Keep the cap closed. Press the safety catch while firmly pulling off the clear base with your other hand. Be careful not to touch the piercing element. Write the discard by date on the label (3 months from the date the cartridge is inserted). 
2. Insert cartridge	
 Insert the narrow end of the cartridge into the inhaler. Place the inhaler on a firm surface and push down firmly until it clicks into place. 
3. Replace clear base	
 Put the clear base back into place until it clicks. Do not remove the clear base or the cartridge after it has been put together. 
4. Turn	
 Keep the cap closed. Turn the clear base in the direction of the arrows on the label until it clicks (half a turn). 
5. Open	
 Open the cap until it snaps fully open. 
6. Press	
 Point the inhaler toward the ground. Press the dose-release button. Close the cap. If you do not see a mist, repeat steps 4 to 6 until a mist is seen. After a mist is seen, repeat steps 4 to 6 three more times. After complete preparation of your inhaler, it will be ready to deliver the number of puffs on the label. 

Daily use (T O P)

Turn
 
 Keep the cap closed. Turn the clear base in the direction of the arrows on the label until it clicks (half a turn). 	

Open
 
 Open the cap until it snaps fully open. 	

Press
 
 Breathe out slowly and fully. Close your lips around the mouthpiece without covering the air vents. Point the inhaler to the back of your throat. While taking a slow, deep breath through your mouth, Press the dose-release button and continue to breathe in. Hold your breath for 10 seconds or for as long as comfortable. Repeat Turn, Open, Press (TOP) for a total of 2 puffs. Close the cap until you use your inhaler again. 	

Answers to Common Questions

IT IS DIFFICULT TO INSERT THE CARTRIDGE DEEP ENOUGH:

Did you accidentally turn the clear base before inserting the cartridge? Open the cap, press the dose-release button, then insert the cartridge.

Did you insert the cartridge with the wide end first? Insert the cartridge with the narrow end first.

I CANNOT PRESS THE DOSE-RELEASE BUTTON:

Did you turn the clear base? If not, turn the clear base in a continuous movement until it clicks (half a turn).

Is the dose indicator on the SPIRIVA RESPIMAT pointing to 0 (zero)? The SPIRIVA RESPIMAT inhaler is locked after the labeled number of puffs have been used. Prepare and use your new SPIRIVA RESPIMAT inhaler.

I CANNOT TURN THE CLEAR BASE:

Did you turn the clear base already? If the clear base has already been turned, follow steps “Open” and “Press” under “Daily use” to get your medicine.

Is the dose indicator on the SPIRIVA RESPIMAT pointing to 0 (zero)? The SPIRIVA RESPIMAT inhaler is locked after the labeled number of puffs have been used. Prepare and use your new SPIRIVA RESPIMAT inhaler.

THE DOSE INDICATOR ON THE SPIRIVA RESPIMAT REACHES 0 (ZERO) TOO SOON:

DID YOU USE SPIRIVA RESPIMAT AS INDICATED (2 PUFFS 1 TIME EACH DAY)?

Did you turn the clear base before you inserted the cartridge? The dose indicator counts each turn of the clear base regardless whether a cartridge has been inserted or not.

Did you spray in the air often to check whether the SPIRIVA RESPIMAT is working? After you have prepared SPIRIVA RESPIMAT, no test-spraying is required if used daily.

Did you insert the cartridge into a used SPIRIVA RESPIMAT? Always insert a new cartridge into a new SPIRIVA RESPIMAT.

MY SPIRIVA RESPIMAT SPRAYS AUTOMATICALLY:

Was the cap open when you turned the clear base? Close the cap, then turn the clear base.

Did you press the dose-release button when turning the clear base? Close the cap, so the dose-release button is covered, then turn the clear base.

Did you stop when turning the clear base before it clicked? Turn the clear base in a continuous movement until it clicks (half a turn).

My SPIRIVA RESPIMAT DOES NOT SPRAY:

Did you insert a cartridge? If not, insert a cartridge.

Did you repeat Turn, Open, Press (TOP) less than 3 times after inserting the cartridge? Repeat Turn, Open, Press (TOP) 3 times after inserting the cartridge as shown in steps 4 to 6 under “Prepare for first use”.

Is the dose indicator on the SPIRIVA RESPIMAT pointing to 0 (zero)? You have used up all your medicine and the inhaler is locked.

For more information about SPIRIVA RESPIMAT, including current prescribing information, or a video demonstration on how to use SPIRIVA RESPIMAT, go to www.spiriva.com, or scan the code below. You may also call [name] or (TTY) [name] for further information about SPIRIVA RESPIMAT.

This Instructions for Use has been approved by the U.S. Food and Drug Administration. Distributed by:

Boehringer Ingelheim Pharmaceuticals, Inc., Ridgefield, CT 06877 USA

SPIRIVA® and RESPIMAT® are registered trademarks and are used under license from Boehringer Ingelheim International GmbH

Copyright © 2019 Boehringer Ingelheim
International GmbH ALL RIGHTS
RESERVED

Revised: February 2019
IT5904IB252019
